5.2 SECONDARY ENDPOINTS

5.2.1 Key secondary endpoint

This section is not applicable as no key secondary endpoint has been specified in the protocol.

[figure not shown]
5.2.2 Other Secondary endpoints

[figure not shown]
[figure not shown]
Secondary efficacy endpoints are the same as detailed in Section 5.1.1 of the protocol. Namely, they are the following:

Change from baseline in the ADCS-ADL (Alzheimer's Disease Cooperative Study/Activities of Daily Living) score after 12 weeks of treatment.

Change from baseline CDR-SB (Clinical Dementia Rating – Sum of Boxes) after 12 weeks of treatment

Change from baseline in ADAS-Cog11 (Alzheimer's Disease Assessment Scale cognitive subscale) total score after 12 weeks of treatment.

6 GENERAL ANALYSIS DEFINITIONS

6.1 TREATMENTS

For regimen details refer to Section 3.1 of the CTP.

The treatments and treatment periods are defined as follows:

Table 6.1: 1 Treatment descriptions

TPATT	Long Name	Short Name
A	BI 409306 10 mg QD	BI 10mg QD
B	BI 409306 25 mg QD	BI 25mg QD
C	BI 409306 50 mg QD	BI 50mg QD
D	BI 409306 25 mg BID	BI 25mg BID
E	Placebo	Placebo
F	Donepezil 5mg/10mg QD	Donepezil

Table 6.1: 2 Definition of analyzing treatment period

Label	Interval	Start Date	Start time
Screening	Screening	Date of informed consent	00:00
Placebo Run-in (PBORI)	Run-in	Date of first administration of run-in medication	Time of first administration of run-in medication 12:00 if missing
BI 409306 10mg QD BI 409306 25mg QD BI 409306 50mg QD BI 409306 25mg BID Placebo Donepezil 5mg/10mg QD	Treatment	Date of first administration of study drug	Time of first administration of study drug 12:00 if missing
Post-treatment	Post-treatment	Date of last intake of study drug + X+1 (see definition of X below)	00:00
Post-study	Post-study	Start date = Last contact date, defined as the maximum of (Trial completion date, last study drug intake + X) +1	00:00

For safety analyses, data up to 7 days after last treatment intake will be considered as on treatment for AEs and for laboratory values. To clarify;

- Screening: starts from the date of informed consent to the date of first administration of run-in medication.
- Placebo run in period: starts from the date of first administration of run-in medication to the date of first administration of randomised study drug.
- On treatment: From the first intake of randomised study drug to last intake of randomised study drug + X days, where X=7 days for safety laboratory and AE.
- Post-treatment: From end of on-treatment period until last contact. Last contact date is defined in Table 6.1: 1. Post treatment period is not applicable for patients with last contact equal to 'last intake + X + 1 days' where X is 7 days as previously specified.
- Post study: From day after last contact defined in [Table 6.1: 1](#). If period starts at end of on-treatment period then post-treatment period is not applicable.

6.2 IMPORTANT PROTOCOL VIOLATIONS

Important protocol violations (IPV) affecting subjects' rights will be identified separately from those affecting analysis sets in the study report. Patients with important PVs that could potentially impact efficacy endpoints will be excluded from the PPS (Refer to [Section 6.3](#)).

The protocol violations are listed in the [Table 6.2: 1](#) below. They will be reviewed at Medical Quality Review Meetings (MQRMs) conducted periodically based on data accumulated during the trial. A list of protocol deviations will be discussed at the blinded report planning meeting (BRPM).

If the data show other important PVs, this table will be supplemented accordingly at MQRMs or BRPMs or through team review of the manual PV log. The decision whether a patient will be excluded from the analysis will be made at the final BRPM prior to DBL.

Table 6.2: 1 important protocol violations

Category/ Code	Description	Example/Comment	Excluded from PPS	Automatic /Manual
A	Entrance criteria not met			
A1	Inclusion criteria not met			
A1.1	Patient younger than 55 years of age	Inclusion criteria 7 not met as specified in the protocol.	Yes	Automatic
A1.2	Diagnosis of mild Alzheimer's Dementia not met	Inclusion criteria 1 not met as specified in the protocol.	Yes	Automatic
A1.3	Inadequate MMSE or ADAS-cog11 or CDR score	Inclusion criteria 2 not met as specified in the protocol.	Yes	Automatic
A1.4	Previous or current use of AD medication requirement not met.	Inclusion criteria 6 not met as specified in the protocol.	Yes	Automatic
A1.5	Inadequate education and language	Inclusion criteria 5 not met as specified in the protocol.	Yes	Automatic
A1.6	Inadequate study partner reliability	Inclusion criteria 4 not met as specified in the protocol.	Yes	Automatic
A2	Exclusion criteria met			
A2.1	Alzheimer's Dementia secondary disorder	Exclusion criteria 1 met as specified in the protocol.	Yes	Automatic
A2.2	Substantial concomitant cerebrovascular disease	Exclusion criteria 2 met as specified in the protocol.	Yes	Automatic
A2.3	Symptomatic and unstable/uncontrolled conditions	Exclusion criteria 4 met as specified in the protocol.	Yes	Automatic
A2.4	Neurological disease or other psychiatric disorder	Exclusion criteria 6 met as specified in the protocol.	Yes	Automatic
A2.5	Any suicidal behavior in the past 2 years	Exclusion criteria 7 met as specified in the protocol.	No	Automatic
A2.6	Any suicidal ideation of type 4 or 5 in the C-SSRS in the past 3 months	Exclusion criteria 8 met as specified in the protocol.	No	Automatic
A2.7	Participation in AD study less than 3 months from screening, treatment for disease modification or non-prescription medications	Exclusion criteria 9 met as specified in the protocol.	Yes	Automatic
A2.8	Known history of HIV infection	Exclusion criteria 11 met as specified in the protocol.	Yes	Automatic
A2.9	Prohibited drugs within 3 months prior to study participation	Exclusion criteria 17 met as specified in the protocol.	Yes	Automatic

Proprietary confidential information © 2017 Boehringer Ingelheim International GmbH or one or more of its affiliated companies

Table 6.2: 1 (continued) important protocol violations

Category /Code	Description	Example/Comment	Excluded from PPS	Automatic /Manual
A2.10	Uncompensated hearing loss	Exclusion criteria 21 met as specified in the protocol.	Yes	Automatic
B	Informed consent not available/not done			
B1	Informed consent not available/not done	Informed consent date missing; no signature on ICF	Exclude from All	Automatic /Manual
B2	Informed consent too late	
Check if informed consent date (actual consent date) was prior or on Visit 1.
 
Applicable to all informed consents. Date of informed consent was after the date of any study-related procedure.
 
If patient signed the wrong version of ICF and then signed the correct version of ICF with the date after screening, it is still deemed as IPV
	No	Automatic /Manual
C	Trial medication and randomization			
C1	Incorrect trial medication taken			
C1.1	Incorrect trial medication taken during study	
Any deviation. Check whether the medication packages dispensed (med. Numbers entered into RDC) has the correct content (to be seen from the med. number list that was the basis for packaging). If content was correct, the deviation will only be noted. Otherwise, the cases will be described individually and possibly excluded.
 
In addition, check whether the dispensed packages match the randomized treatment of the patient (IRT assignment). If not, and if treated consistently throughout the trial, analyze as treated.
	Yes	Automatic
C2	Randomization order not followed			

Proprietary confidential information © 2017 Boehringer Ingelheim International GmbH or one or more of its affiliated companies

Table 6.2: 1 (continued) important protocol violations

Category /Code	Description	Example/Comment	Excluded from PPS	Automatic /Manual
C2.1	Error by the vendor who implemented the randomization scheme	E.g., the same randomization number was given to different patients or the assignment of duplicate medication numbers or incorrect medication numbers. Verify by comparing the medication numbers and randomization numbers from IRT. If a patient actually receives the correct medication despite the wrong kit, they will not be excluded from the PPS. Vendor to check before unblinding.	Yes	Manual
C3	Non-compliance with study medication			
C3.1	Non-compliance with study medication	Compliance < 80% or >120 %	Yes if <80%	Automatic /Manual
D	Concomitant medication			
D1	Prohibited medication use before the treatment period of the trial	To be determined on a case by case basis.	Yes	Automatic /Manual
D2	Prohibited medication use during the conduct of the trial	To be determined on a case by case basis.	Yes	Automatic /Manual
E	Trial specific protocol violations			
E1	Negative pregnancy test result not obtained during the study participation		No	Automatic
E2	Treatment not discontinued due to HR elevation as described in CTP section 3.3.4.		No	Automatic
E3	Study partner change during study.		Yes	Automatic
E4	Assessments administered by unqualified rater		Yes	Manual
E5	C-SSRS not administered at every visit		No	Automatic

Proprietary confidential information © 2017 Boehringer Ingelheim International GmbH or one or more of its affiliated companies

Table 6.2: 1 (continued) important protocol violations

Category /Code	Description	Example/Comment	Excluded from PPS	Automatic /Manual
F	Incorrect timing of endpoint measurements			
F1	Incorrect timing - assessments			
F1.1	Assessment order not followed	NTB not administered in order specified in CTP	Yes	Automatic
F1.2	Rater switch on primary endpoint	NTB not administered by same rater	Yes	Manual
F2	Incorrect timing – times of measurements			
F2.1	Assessment of NTB outside of window between visits	NTB assessment time >2 hour from Visit 3 NTB assessment time.	Yes	Automatic

KEY: PPS – Per Protocol Set

6.3 PATIENT SETS ANALYSED

SCR - Screened set: All patients screened for the trial, with informed consent given and who completed at least one screening procedure at Visit 1.

RS- Randomized set: This patient set includes all patients who signed the informed consent form and were also randomized, regardless whether the patient was treated with trial medication or not.

TS-Treated set: All patients who were randomized and treated with at least one dose of study drug.

FAS- Full analysis set: The full analysis set (FAS) will consist of all randomized patients who were treated with at least one dose of study drug and had a baseline and at least one post baseline on treatment primary endpoint NTB assessment (or secondary endpoint assessment). The FAS will be used for the primary analyses (and secondary analyses).

PPS- Per protocol set: All patients in the FAS without important protocol deviations that impact efficacy assessments. No analyses for the CTR are planned using the PPS set.

The SCR,RS and TS will be used to populate patient disposition and the TS will be used for demographics, baseline characteristics, treatment exposure, and safety analyses (including adverse events, laboratory measurements, vital signs, and ECG). Safety analyses will assign patients to the treatment group based on the treatment received.

If a patient erroneously receives the wrong dose of study drug, the patient's efficacy data will be analyzed in the randomized treatment group and the patient's safety data will be analyzed in the actual treatment group.

The efficacy analyses will follow the intention-to-treat (ITT) principle in assigning patients to treatment groups. I.e., efficacy analyses will be analyzed as randomized using the FAS.

If a patient receives a different study drug than randomized, this will be noted as an IPV.

Proprietary confidential information © 2017 Boehringer Ingelheim International GmbH or one or more of its affiliated companies

Table 6.3: 1 Patient sets analyzed

Class of endpoint	Patient set			
	SCR	RS	TS	FAS
Primary				OC
Secondary				OC
Further				OC
Safety endpoints			OR	
Disposition	OR ¹	OR ¹	OR ¹	
Demographic		OR ²	OR	
Baseline endpoints		OC		
Disclosure tables	OR		OR	

1) Disposition table requires multiple patient sets to populate

2) Additional table for clinical trial disclosure requirements

Note: For definitions of OC (Observed Case) or OR (Original Results) refer to section 6.6.

Note that the number of patients with available data for an endpoint may differ. For details, see section 6.6.

6.5 POOLING OF CENTRES

This section is not applicable because centre/country is not included in the statistical model.

6.6 HANDLING OF MISSING DATA AND OUTLIERS

Original result (OR) analysis

Original result analysis implies the analysis of data exactly as observed. OR analysis will be performed on endpoints that are not meaningful to apply any imputation rule on them for replacing the missing values.

6.6.1 Missing efficacy data

NTB

Details on scoring with missing items are described in [section 9.1](#).

ADAS-Cog11

Proprietary confidential information © 2017 Boehringer Ingelheim International GmbH or one or more of its affiliated companies

If a patient has 3 or fewer missing ADAS-Cog/11 items, the following algorithm will be used to compute the ADAS-Cog/11 total score:

Total score = [(total score from completed items) / (maximum total score for completed items)]*(maximum total score[=70] for all items in the scale)

If there are more than 3 missing ADAS-Cog/11 items, ADAS-Cog/11 score will be considered missing at that time point.

ADCS-ADL

For ADCS-ADL, if <30% of the items are missing, the total score will be imputed. The sum of the nonmissing items will be prorated to the sum of total items. The imputed number will be rounded up to the nearest integer. If the nearest integer is greater than the maximum possible score, the imputed score will be equal to the maximum score. If >30% of the items are missing, the total score at that visit will be considered missing. For e.g Total score = [(total score from completed items) / (maximum total score for completed items)]*(maximum total score[=78] for all items in the scale) Supplementary material for [8].

CDR-SB

If only 1 box (of 6) of the CDR is missing, the sum of the boxes will be imputed by prorating the sum from the other 5 boxes. If the score from more than 1 box is not available, the CDR-SB at that visit will be considered missing. For e.g Total score = [(total score from completed items) / (maximum total score for completed items)]*(maximum total score[=18] for all items in the scale) Supplementary material for [16].

Observed cases (OC) analysis

For all efficacy endpoints using MMRM analyses, it is planned to analyze only the available data that were observed while patients were on treatment, i.e., excluding the missing data. In other words, OC analysis will be performed and missing data in this analysis will not be replaced.

The following imputation methods will be used if the rate of missing data is greater than 5%.

The method below will be used for the endpoints using ANCOVA analyses.

Last observation carried forward (LOCF) analysis

The last observation on-treatment need not necessarily be a value selected as a visit value if multiple measurements were performed within a time window for a visit. In this case the last on-treatment value within the time window will be carried forward, while the visit value can be the value that was observed closest to the planned visit date or the first value observed in the time window. See [Table 6.7: 2](#) for further details.

Baseline Observation Carried Forward (BOCF)

As part of the LOCF technique, baseline values will be carried forward if no post-baseline value is available.

Proprietary confidential information © 2017 Boehringer Ingelheim International GmbH or one or more of its affiliated companies

6.6.2 Missing safety data and other data

In general, missing data will not be imputed and only observed values will be analyzed. Data of patients who withdrew after the screening examination or were not treated will be only listed.

6.6.3 Missing AE dates and times

Missing or incomplete AE dates are imputed according to BI standards (see “Handling of missing and incomplete AE dates”) (2).

6.6.4 Missing plasma concentrations and pharmacokinetic parameters

Missing data and outliers of PK data are handled according to (1).

6.7 BASELINE, TIME WINDOWS, AND CALCULATED VISITS

For efficacy, the baseline is defined as the pre-treatment observation at Visit 3. All other baseline variables will be observed from Visit 1.

For laboratory safety measurements, the last values prior to study drug administration will be considered as baseline values.

The midpoint between two on-treatment visits defines the end of a time window, with the midpoint being included in the time window of the preceding visit.

Table 6.7: 1 Time windows for all pre/on-treatment safety visits

Visit number	Visit label	Planned days	Interval (actual days on treatment)
1	Screening	-28	$(-\infty, \text{PBORI}-1]$
2	Placebo Run-in period	-14	$[\text{PBORI}, \text{TREATMENT}-1]$
3	Baseline	1	$[\text{NA}, 1]$
4a	Week 1	8	$[2, 11]$
4b	Week 2	15	$[12, 18]$
4c	Week 3	22	$[19, 25]$
5	Week 4	29	$[26, 43]$
6	Week 8	57	$[44, 73]$
EOT	Week 12	85	$[74, 99]$
FU	Follow-up	113	$[100, \text{Study drug stop date} + 7 \text{ days}]$

These time windows are defined based on the planned number of days after the date of first administration of study drug. Reasons to base the time windows on the actual treatment start date rather than the randomisation date are:

- If first intake of study drug shows a large delay by e.g. more than one week after the date of randomisation, a measurement taken four weeks after randomisation rather reflects the drug effect after three weeks than after four weeks and thus may underestimate the treatment effect at this visit.

Proprietary confidential information © 2017 Boehringer Ingelheim International GmbH or one or more of its affiliated companies

- With large delays of the introduction of study drug after the randomisation, the time window for the first on-treatment visit could include times the patient was not yet on study drug.

Table 6.7: 2 Time windows for on-treatment efficacy measurement scheduled for each on treatment visit

Visit Number	Visit label	Planned days	Time window (actual days on treatment)	
			Start	End ^A
3	Baseline	1	NA	1 ^B
5	Week 4	29	2	57
EOT	Week 12	85	58	Study drug stop date + 7 days

A In case of premature discontinuation of the study drug an EOT Visit has to be performed. If such an EOT Visit falls into the time window of a previous visit, measurements will be assigned to this previous visit and the visit value will be determined as described below. In this case the time window for the visit that includes EOT Visit will end 7 days after the study drug stop date, including Day 7.

B Only values taken prior to the start of treatment with randomised study drug can be considered baseline values. Time windows will be used for assignment of measurements to scheduled visits.

Repeated and unscheduled efficacy and safety measurements will be

assigned to the nominal visits and listed in the subject data listing (SDL) according to the time windows described above.

If there are several safety laboratory values in one time window on treatment, the worst of these will be selected for the by-visit analyses.

For efficacy measurements, only one observation per time window will be selected for analysis at an on-treatment visit – the value will be selected which is closest to the protocol planned visit day. If there are two observations which have the same difference in days to the planned day or if there are two observations on the same day, the first value will be used. If an observation is available on the last day of treatment, this observation will be preferably selected over any later observation that is still within the time window.

Note: for LOCF imputation, the last observed on-treatment value will be carried forward, whether or not it was selected in the previous time window. For more details on LOCF refer to [section 6.6](#).

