## FLOW CHART

Trial Period	Screening	Placebo Run-in Period	Treatment Period							Follow-up
			3 Baseline	4a 	4b 	4c 	5	6	EOT/ED 	
Visit	1	2		1	2	3	4	8	12	16
Studyweeks	-3	-2		1	2	3	4	8	12	16
Study-Day (or duration during screening/ run-in)	Duration 1-7 days	Duration at least 14 and at most 21 days after screening period	1	8	15	22	29	57	85	EOT +28
Visit window (in days)				±1	±1	±1	±3	±3	+3	±3
Patient information & informed consent signed ████████████████████	X									
Register Patient in IRT	X									
Randomisation (via IRT)			X							
Demographics	X									
Medical history / baseline conditions	X									
In-/exclusion criteria	X	X	X							
Imaging of the Brain 	X									
Concomitant medications	X	X	X	X	X	X	X	X	X	X
Height (screening only)/weight	X								X	X
Vital signs	X		X	X	X 	X 	X	X	X	X
Post Dose Heart Rate Procedure 			X							
Physical examination	X								X	
Neurological examination	X								X	
Resting ECG (digital)	X		X	X	X 	X 	X	X	X	X
Adverse events	X	X	X	X	X 	X 	X	X	X	X
Dispense trial medication 		X	X				X	X		
Collect study drug			X				X	X	X	
Medication Compliance Check			X				X	X	X	
Laboratory tests: Chemistry, haematology, urinalysis	X		X				X	X	X	X
Blood Glucose (Onsite) 	X		X				X		X	
████████████████████			█					█		
████████████████████			█						█	
Urine drug screen	X								X	
Urine pregnancy test 	X		X				X	X	X	
Vitamin B12 and folate	X								X	
RPR (FTA, if RPR positive)	X									
Prospective Suicidality Monitoring										
C-SSRS	X 	X 	X 	X 	X 	X 	X 	X 	X 	X 

Proprietary confidential information.

© 2017 Boehringer Ingelheim International GmbH or one or more of its affiliated companies. All rights reserved.

This document may not - in full or in part - be passed on, reproduced, published or otherwise used without prior written permission.

Trial Period	Screening	Placebo Run-in Period	Treatment Period							Follow-up
			3 Baseline	4a 	4b 	4c 	5	6	EOT/ED 	
Visit	1	2								FU
Studyweeks	-3	-2		1	2	3	4	8	12	16

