Study-Day (or duration during screening/ run-in)	Duration 1-7 days	Duration at least 14 and at most 21 days after screening period	1	8	15	22	29	57	85	EOT +28
Visit window (in days)				±1	±1	±1	±3	±3	+3	±3
Neuropsychological Rating Scales										
MMSE	X									
CDR	X									
CDR-SB			X 				X		X	
NTB			X 				X		X	
ADCS-ADL			X 						X	
ADAS-cog 11	X		X 						X	

 Prior to any study related procedure

 Results of a MRI or CCT-scan have to be available before visit 2. Please refer to exclusion #1 for further details. If a CCT or MRI cannot be obtained within the given visit window the duration of the screening period may be extended to a maximum of 21 days (if needed).

 The baseline vital signs (supine pulse rate after 5 minutes of rest and systolic/diastolic blood pressure) will be measured before the first dose is taken. Additional vital signs assessments will be performed at the time points of post-dose PK sampling given in table 10.1.1:1 until 70-110 minutes post-dose (See section 5.2.5 and section 6.2 for details).

 At all visits, the respective kit number has to be allocated to the patient via IRT

 Only for patients with antidiabetic therapy (see section 6.2 for details).

[REDACTED]

 Local urine pregnancy test (or blood test if required by local regulations) in women of child bearing potential. More frequent testing may be performed if required by local regulations.

 Columbia Suicide Severity Rating Scale baseline/screening scale

 Columbia Suicide Severity Rating Scale baseline since-last-visit scale

 Also to be completed for patients who are withdrawn or who have discontinued the trial early; in case of early termination visit 7 should be performed no later than 7 days after the last study drug intake (visit FU four weeks later).

 If the assessments at visit 4a do not show clinically relevant findings compared to baseline and if deemed clinically acceptable by the investigator then visits 4b and 4c may be performed as phone contacts. Attendance of the study partner is not necessarily required during visits 4 a-c. ECG and vital signs are only to be performed at clinic visits.

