### 5.2.5.2 Vital signs

Vital signs (systolic/diastolic blood pressure (including orthostatic measurement as outlined below), supine pulse rate after 5 minutes rest) will be recorded at all the study visits as described in the [Flow Chart](#), including the early End of Treatment Visit and the Follow-up Visit (4 weeks after the end of treatment). Body weight will be measured at the visits indicated in the flow chart and the same scale has to be used for all measurements. The height is measured only at visit 1 (screening).

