### Visits 5, 6 and EOT/ED

- Study procedures have to be completed according to the [Flow Chart](#).
- Collect returned medication at every visit prior to dispensing new medication
- Neuropsychological assessments and collection of urine and blood for laboratory testing [REDACTED] must be performed prior to administration of study medication
- For diabetic patients with antidiabetic therapy: exclusion of hypoglycemia for the period of the neuropsychological assessment (documented plasma glucose concentration  $\geq 90$  mg/dl (5mmol/l) at the beginning and directly after the assessment).
- Administer the following neuropsychological assessments in the following order:
  - CDR-SB (V5 and EOT)
  - NTB (V5 and EOT)
  - ADCS-ADL (EOT)
  - ADAS-cog11 (EOT)
- Administration of C-SSRS (baseline since last visit scale)
- The intake of trial medication and handling of medication blisters should be discussed and (if deemed necessary) re-trained with the patient and the caregiver. The dose of trial medication should be taken by the patient after the neuropsychological assessments have been administered.
- [REDACTED]
- Blood pressure must always be measured before taking any blood sample
- Laboratory samples will be collected as described in [Flow chart](#).
- New medication kit must be dispensed at Visits 5 and Visit 6 and IRT must be contacted at those visits to obtain medication kit numbers to be dispensed.
- Instruct patient NOT to take study medication on the morning of next trial visits.
- Visit EOT/ED is the end of treatment visit. Study medication will not be taken at Visit EOT/ED.

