7.8.2 Laboratory data

The analyses of laboratory data will be descriptive in nature and will be based on BI standards (5).

Baseline for safety laboratory parameters will be the last available measurement before the start of randomized study drug.

Laboratory measurements taken up to 7 days after the last administration of randomised study drug will be considered as on-treatment.

Only patients with at least one available on-treatment value will be included in the analysis of an individual laboratory parameter. All individual data will be presented in listings.

Study visits will be presented by the Visit labels in [Table 6.7.1](#),

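### SAP Table 6.7:1 gives the Follow-up visit a window that can never contain it, and ends the Week 8 window two days past the SAP's own midpoint

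*SAP*

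**What the plan says.** **SAP 6.7.** Table 6.7:1 is headed "Time windows for all pre/on-treatment safety visits". Days are counted from the first administration of study drug. The text above the table ends each window at the midpoint between two on-treatment visits and gives the midpoint to the earlier visit. The rows at issue are Week 8 (planned Day 57, window [44, 73]), Week 12/EOT (planned Day 85, window [74, 99]) and Follow-up (planned Day 113, window from Day 100 to study drug stop date + 7 days).

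**Protocol timing.** The Flow Chart puts EOT at Day 85 with a window of +3 days, and Follow-up at EOT + 28 with ±3 days. Section 6.2.2 says "Study medication will not be taken at Visit EOT/ED". For early discontinuation, Flow Chart footnote 11 says "visit 7 should be performed no later than 7 days after the last study drug intake (visit FU four weeks later").

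**What is collected at Follow-up.** The Flow Chart row "Laboratory tests: Chemistry, haematology, urinalysis" is marked at that visit, as is the resting ECG. Protocol 5.2.5.2 has vital signs recorded at all scheduled visits, "including the early End of Treatment Visit and the Follow-up Visit (4 weeks after the end of treatment").

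**How it is displayed.** For laboratory data, SAP 7.8.2 says "Study visits will be presented by the Visit labels in" Table 6.7:1. SAP 6.1 extends the on-treatment period to last intake + X days and gives X = 7 for laboratory data and adverse events. Its Post-treatment interval starts at "Date of last intake of study drug + X+1".

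**The concern.** The upper limit of the Follow-up row is tied to the end of dosing, while the visit is by design about four weeks after dosing ends. If the limit closes before the window opens, the one scheduled off-drug safety assessment has no label in the table that drives the by-visit displays. The programmer then has to improvise.

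The same table puts no stop-date limit on the earlier windows. A patient who stops early has the follow-up visit early as well, and that visit can fall inside a window meant for on-treatment data.

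The Week 8 limit is a plainer matter: the listed day does not follow from the rule printed above the table. Under SAP 6.7 the worst laboratory value in an on-treatment window is the one selected, so the boundary decides which visit's summary an unscheduled value enters.

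**Working it through.** **1. The SAP's own window ends.** Rule: end = midpoint of the two planned days, rounded down to a whole day.

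| Pair of planned days | Midpoint | End by rule | End in table |
|---|---|---|---|
| 8, 15 | 11.5 | 11 | 11 |
| 15, 22 | 18.5 | 18 | 18 |
| 22, 29 | 25.5 | 25 | 25 |
| 29, 57 | 43 | 43 | 43 |
| 57, 85 | 71 | **71** | **73** |
| 85, 113 | 99 | 99 | 99 |

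Five of six ends reproduce, so the rule is being read correctly and Week 8 is an isolated slip of 73 − 71 = 2 days. Rounding cannot explain it, because the midpoint is already a whole day. An end of 73 would need the next visit planned at Day 89 (2 × 73 − 57) or Day 90, and the schedule has neither. Visit 6 on schedule is Day 57 ± 3 = 54-60 and EOT is Day 85-88, so no on-schedule visit falls on Days 72-73.

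**2. Follow-up window, on schedule.**
- EOT: Day 85 to 88. No dose is taken at EOT, so last intake is the day before: Day 84 to 87.
- Upper limit, stop + 7: 84 + 7 = 91 to 87 + 7 = 94.
- The window is therefore [100, 91] to [100, 94]. It is empty, with the end 100 − 94 = 6 to 100 − 91 = 9 days before the start.
- It is non-empty only if stop + 7 ≥ 100, that is, last intake on Day 93 or later. That is 93 − 87 = 6 days beyond the latest on-schedule last intake.
- The visit falls on Day 85 + 25 = 110 to 88 + 31 = 119. That is 1 + 25 = 26 to 1 + 31 = 32 days after last intake, or 19 to 25 days past stop + 7.

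**3. Follow-up window, any protocol-compliant schedule.** With EOT 0 to 7 days after last intake and Follow-up 25 to 31 days after EOT, the visit is 25 to 38 days after last intake, or 18 to 31 days past stop + 7. A count over last-intake days 1 to 119, with every allowed EOT and Follow-up day, put no follow-up visit inside the window; the smallest gap was 25 days.

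**4. Where an early discontinuer's follow-up goes.** Since the visit is 25 to 38 days after last intake, it can fall in the Week 12 window [74, 99] when last intake is between Day 74 − 38 = 36 and Day 99 − 25 = 74. Example: last intake Day 55, EOT Day 60, Follow-up Day 60 + 28 = 88. Day 88 lies in [74, 99], yet the patient has been off drug for 88 − 55 = 33 days. For laboratory data SAP 7.8.2 keeps such a value out of the on-treatment period. For vital signs and ECG no such cut-off is stated: X = 7 is given for laboratory data and adverse events, and the stop + 7 truncation in footnote A is marked on the efficacy table (Table 6.7:2) only.

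**5. Efficacy windows.** In Table 6.7:2 the midpoint (29 + 85)/2 = 57 matches the listed end for Week 4. Nothing there is affected.

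**The case against.** The best defence of the Follow-up row is that the table covers pre- and on-treatment visits, that stop + 7 agrees with the SAP's on-treatment definition, and that off-drug values belong to the Post-treatment interval of SAP 6.1. Individual laboratory data are listed in any case, protocol 7.3.3 bases the laboratory shift tables on the last on-treatment value, and laboratory displays also follow a sponsor standard that is not in the documents. This stands as far as it goes: no value is lost, and a gap is shown for Table 6.7:1, not for the whole reporting system. But the SAP lists Follow-up at Day 113 and then sets a limit that excludes it. The Post-treatment interval supplies no visit label, and a listing is not a by-visit summary. The column heading, which counts actual days on treatment, hints that off-drug values were not meant for Week 12, but no cut-off for vital signs or ECG is written.

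On Week 8, it is fair to say that two days change nothing for scheduled data.

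A reader might also infer that the vital-sign baseline is in conflict, because SAP 6.7 says all other baseline variables come from Visit 1. The documents do not support that. Protocol 7.3.3, which SAP 7.8 adopts, names baseline separately from screening; the Flow Chart and Table 6.7:1 both label Visit 3 as Baseline; and Flow Chart footnote 3 takes the baseline vital signs before the first dose. The Visit 1 sentence is loosely worded, no more.

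Nor do the Day 1 post-dose pulse readings enter the baseline merely because that window has no stated pre-dose limit. Footnote B is generally worded and restricts baseline to values before randomised treatment, and Table 6.1:2 starts treatment at the time of first dose.

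**Conclusion.** Two rows of Table 6.7:1 are wrong as written. The Follow-up window is empty on schedule and cannot hold the follow-up visit on any protocol-compliant schedule. Week 8 overruns the SAP's own midpoint by 2 days.

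The point is minor. It concerns descriptive safety summaries; no hypothesis test, efficacy window or primary result changes, and a reader who inferred otherwise would be mistaken. The practical effects are three:
- Scheduled off-drug laboratory, vital-sign and ECG values cannot carry the Follow-up label. The only values that could are on-treatment values from patients still dosing on Day 93 or later.
- Off-drug vital signs and ECG from some patients who stop between Day 36 and Day 74 can be counted under Week 12. How many is unknown. The 10% and 20% dropout assumptions in protocol 7.6 would give about 35 to 71 of 354 patients stopping at any time (354 × 0.10 and 354 × 0.20), and only part of these would fall in that range.
- Unscheduled or early-termination values on Days 72-73 go to Week 8 instead of Week 12.

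The day counts assume that the last dose is taken the day before EOT and that visits keep to the protocol windows. If a dose were taken on Day 88, the window would end on Day 95 and still be empty.

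**What to change.** 1. Define Follow-up as a post-treatment window that starts after stop date + 7, in line with the start of the Post-treatment interval in SAP 6.1, and remove the stop + 7 upper limit. On schedule it would then open on Day 92-95 (84 + 8 to 87 + 8) and hold the visit on Day 110-119.
2. End each on-treatment safety window at the earlier of its listed limit and stop date + 7, and state that this cut-off covers vital signs and ECG as well as laboratory data. In the example above, Week 8 would end on Day 62 (55 + 7), Week 12 would not apply, and the Day 88 values would be labelled Follow-up.
3. Set Week 8 to [44, 71] and Week 12 to [72, 99].
4. As a clarification only, limit the Visit 1 baseline sentence in SAP 6.7 to characteristics collected at screening alone, so that it agrees with the Visit 3 pre-dose vital-sign baseline.

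The cost is SAP wording and table programming. No new data are needed.
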